7.4 SAFETY REPORTING CRITERIA TO THE PHARMACEUTICAL COLLABORATORS

All events listed below must be reported in the defined timelines to [contact].

The CCR Office of Regulatory Affairs will send all reports to the manufacturer as described below.

7.4.1 Reporting to Astellas

The Investigator should complete and submit an SAE Medwatch 3500 Form, containing all information that is required by the Regulatory Authorities, to Astellas by either e-mail or fax within 24 hours of awareness whether or not related to the study drug. If submission of this SAE by email or fax or is not possible within 24 hours, the local drug safety contact (IRB, Investigator, etc.) should be informed by phone.

The SAE documentation, including the Medwatch 3500 Form and available source records, should be emailed or faxed to:

Astellas Pharma Global Development – United States

Version Date: 12/5/17

Abbreviated Title: Enzalutamide in non-met CSPC

Email: [contact]

[contact]

The following minimum information is required:

- Study number/IIT regulatory identifier
- Subject number, sex and age
- The date of report
- A description of the SAE (event, seriousness of the event)
- Causal relationship to the study drug

Follow-up information for the event should be sent within 7 days as necessary.

7.4.2 Reporting to Bavarian Nordic, Inc.

The investigator should also submit all safety reports that are sent to the FDA using the Medwatch 3500 Form to:

Bavarian Nordic, Inc.

Email: [contact];

Fax number for pharmacovigilance at BN: [contact]

Attention: [name]

7.5 INSTITUTIONAL BIOSAFETY COMMITTEE (IBC) REPORTING CRITERIA

7.5.1 Serious Adverse Event Reports to OSP/IBC

The Principal Investigator (or delegate) will notify IBC of any unexpected fatal or life-threatening experience associated with the use of PSA-TRICOM Vaccine as soon as possible but in no event later than 7 calendar days of initial receipt of the information. Serious adverse events that are unexpected and associated with the use of the PSA-TRICOM Vaccine, but are not fatal or life-threatening, must be reported to the NIH IBC as soon as possible, but not later than 15 calendar days after the investigator's initial receipt of the information. Adverse events may be reported by using the FDA Form 3500a.

7.5.2 Annual Reports to IBC

Within 60 days after the one-year anniversary of the date on which the IBC approved the initial protocol, and after each subsequent anniversary until the trial is completed, the Principal Investigator (or delegate) shall submit the information described below. Alternatively, the IRB continuing review report can be sent to the IBC in lieu of a separate report. Please include the IBC protocol number on the report.

7.5.2.1 Clinical Trial Information

A brief summary of the status of the trial in progress or completed during the previous year. The summary is required to include the following information:

- the title and purpose of the trial
- clinical site
- the Principal Investigator
- clinical protocol identifiers;
- participant population (such as disease indication and general age group, e.g., adult or pediatric);
- the total number of participants planned for inclusion in the trial; the number entered into the trial to date whose participation in the trial was completed; and the number who dropped out of the trial with a brief description of the reasons
- the status of the trial, e.g., open to accrual of subjects, closed but data collection ongoing, or fully completed,
- if the trial has been completed, a brief description of any study results.

7.5.2.2 Progress Report and Data Analysis

Information obtained during the previous year's clinical and non-clinical investigations, including:

- a narrative or tabular summary showing the most frequent and most serious adverse experiences by body system
- a summary of all serious adverse events submitted during the past year
- a summary of serious adverse events that were expected or considered to have causes not associated with the use of the gene transfer product such as disease progression or concurrent medications
- if any deaths have occurred, the number of participants who died during participation in the investigation and causes of death
- a brief description of any information obtained that is pertinent to an understanding of the gene transfer product's actions, including, for example, information about dose-response, information from controlled trials, and information about bioavailability.

7.6 DATA AND SAFETY MONITORING PLAN

7.6.1 Principal Investigator/Research Team

The Principal Investigator, lead associate investigator and the research nurse will meet weekly at each clinic to review all adverse events for each subject in this trial and to determine dose limiting toxicities and escalation rules. Unexpected adverse events and/or serious adverse events will be reported to the NCI's Institutional Review Board (IRB) and sponsor/FDA as outlined above. If trends are noted and/or risks warrant it, accrual will be interrupted, dose levels expanded and/or the protocol and/or consent will be modified accordingly.

All data will be collected in a timely manner and reviewed by the principal investigator or a lead associate investigator. Adverse events will be reported as required above. Any safety concerns,

new information that might affect either the ethical and or scientific conduct of the trial, or protocol deviations will be immediately reported to the IRB using iRIS and to the Sponsor.

The principal investigator will review adverse event and response data on each patient to ensure safety and data accuracy. The principal investigator will personally conduct or supervise the investigation and provide appropriate delegation of responsibilities to other members of the research staff.

7.6.2 Sponsor Monitoring Plan

As a sponsor for clinical trials, FDA regulations require the CCR to maintain a monitoring program. The CCR's program allows for confirmation of: study data, specifically data that could affect the interpretation of primary study endpoints; adherence to the protocol, regulations, and SOPs; and human subjects protection. This is done through independent verification of study data with source documentation focusing on:

- Informed consent process
- Eligibility confirmation
- Drug administration and accountability
- Adverse events monitoring
- Response assessment.

The monitoring program also extends to multi-site research when the CCR is the coordinating center.

This trial will be monitored by personnel employed by an NCI contractor. Monitors are qualified by training and experience to monitor the progress of clinical trials. Personnel monitoring this study will not be affiliated in any way with the trial conduct. Safety Monitoring Committee (SMC)

This protocol will require oversight from the Safety Monitoring Committee (SMC). Initial review will occur as soon as possible after the annual NCI-IRB continuing review date. Subsequently, each protocol will be reviewed as close to annually as the quarterly meeting schedule permits or more frequently as may be required by the SMC. For initial and subsequent reviews, protocols will not be reviewed if there is no accrual within the review period. Written outcome letters will be generated in response to the monitoring activities and submitted to the Principal investigator and Clinical Director or Deputy Clinical Director, CCR, NCI.

8 STATISTICAL CONSIDERATIONS

8.1.1 Cohort 1

The primary objective of this study is to compare the change in the growth rate in the two arms from the time of discontinuation of enzalutamide (3 months after enrollment) to 4 months after completing enzalutamide therapy +/- PSA-TRICOM (7 months after enrollment). With growth rate changes obtained on all patients on both arms, and if the growth rate changes in the two arms had the same standard deviation, with 17 patients per arm, there would be 80% power to detect a difference between the arms equal to 1 SD of the difference from baseline to 7 months with a two-tailed 0.05 significance level two-group t-test. Thus, a total of 34 evaluable patients

are required for analysis. To allow for a small number of patients who do not develop a 25% decline in PSA after 3 months, additional patients will be randomized if necessary to obtain a minimum of 17 evaluable patients on each arm. In order to allow for a small number of such patients, the accrual ceiling will be 38.

Patients will be stratified based a doubling time of greater than or less than 6 months.

Secondary endpoints will be compared between the two arms using appropriate non-parametric tests, such as a Wilcoxon rank sum test. Results will be presented without formal adjustment for multiple comparisons but reported in the context of secondary evaluation of a potentially large number of endpoints. The significance of paired hormone level results within arms will be determined by a paired t-test or Wilcoxon signed rank test as appropriate.

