2 ELIGIBILITY ASSESSMENT AND ENROLLMENT

2.1 ELIGIBILITY CRITERIA

2.1.1 Inclusion Criteria

- A. Histopathological documentation of prostate cancer confirmed in the Laboratory of Pathology at the National Institutes of Health (NIH) Clinical

Center, or Walter Reed National Military Medical Center prior to enrollment. If no pathologic specimen is available, patients may enroll with a pathologist's report showing a histologic diagnosis of prostate cancer and a clinical course consistent with the disease.

- B. Biochemical progression defined as follows:
 - For patients following definitive radiation therapy: a rise in PSA of ≥ 2 ng/mL above the nadir (per RTOG-ASTRO consensus criteria).
 - For patients following radical prostatectomy: rising PSA after surgical procedure. (Patients must have a PSA ≥ 2 ng/ml)
- C. ECOG performance status of 0–1 (Karnofsky $\geq 80\%$, see [Appendix A](#)).
- D. Patients must have a PSA doubling time of 12 months or less.
- E. Patients must have a rising PSA as confirmed by 3 values done at least 1 week apart and over no less than 1 month.
- F. Recovery from acute toxicity related to prior therapy, including surgery and radiation, or no toxicity \geq grade 2.
- G. Negative CT scan/MRI and bone scan for metastatic prostate cancer.
- H. Hematological eligibility parameters (within 16 days before starting therapy; see [Appendix D](#)):
 - Granulocyte count $\geq 1000/\text{mm}^3$
 - Platelet count $\geq 100\,000/\text{mm}^3$
 - Hgb ≥ 10 g/dL
- I. Biochemical eligibility parameters (within 16 days before starting therapy):
 - Hepatic function: bilirubin ≤ 1.5 mg/dL (OR in patients with Gilbert's syndrome, a total bilirubin ≤ 3.0), AST and ALT ≤ 2.5 times upper limit of normal.
- J. No other active malignancies within the past 36 months (with the exception of nonmelanoma skin cancers or carcinoma in situ of the bladder) or life-threatening illnesses
- K. Willing to travel to the NIH for follow-up visits.
- L. 18 years of age or older.
- M. Able to understand and sign informed consent.
- N. Baseline testosterone \geq lower limit of normal.
- O. PSA ≤ 20 ng/mL.

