2.4 TREATMENT ASSIGNMENT AND RANDOMIZATION/STRATIFICATION PROCEDURES

Cohorts

Number	Name	Description
1	Cohort 1	Patients with nonmetastatic castration sensitive prostate cancer

Arms

Letter	Name	Description
A	Standard dose enzalutamide alone	Enzalutamide alone administered at the standard dose (160 mg daily)
B	Enzalutamide with PSA-TRICOM	Standard dose enzalutamide with concomitant vaccinia-PSA-TRICOM and then fowlpox-vaccine

Stratifications

Name	Distinct Options	Notes
PSA doubling time less than 6 months	Yes No	

Randomization and Arm Assignment

After confirmation of eligibility at Central Registration Office (CRO), patients in cohort 1 will be randomized on a 1:1 basis between arms A and B, stratifying for PSA doubling time using a computerized randomization process.

CRO staff will send a secured e-mail to Principal Investigator and research nurse with the Verification of Registration of the patient and treatment arm patient is randomized. This process will be completed within 15–30 minutes of faxing the eligibility checklist. CRO will keep track of all randomization data in Clinical Data Registry (CDR) of CRO.

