8.1.3 The regression-growth equation

The equation is $f(t) = \exp(-d * t) + \exp(g * t) - 1$ (A) where \exp is the base of the natural logarithm, $e = 2.7182$, and $f(t)$ is the tumor (or in MTC calcitonin) measurement at time t in days, normalized to (divided by) the tumor measurement at day 0, the time at which treatment is commenced. Rate constant d (decay, in days^{-1}) represents the exponential decrease/regression of the a serum tumor marker (i.e. PSA) signal during therapy. Rate constant g (growth, also in days^{-1}) represents the exponential growth/regrowth of the tumor during treatment. These rate constants may be expressed in terms of half-lives and doubling times. Thus, d equals $\ln_2(0.693)$ divided by the time it takes for the regressing part to shrink by half, whereas g equals \ln_2 divided by the time for the growing component to double. (44)

Two earlier papers depict theoretical curves depicting the separate components of Equation (A) and how these combine together to give the time dependence of the tumor size, f . (44) When the data showed a continuous decrease from the time of treatment start, so that only the regression parameter d was found to differ significantly from zero with $P < 0.05$, Equation (A) was replaced by the following reduced form, with the growth rate constant eliminated: $f(t) = \exp(-d * t)$ (B) When tumor measurements showed a continuous increase, so that only the growth parameter g was found to differ significantly from zero with $P < 0.05$, Equation (A) was replaced by the following reduced form, with the decay constant eliminated: $f(t) = \exp(g * t)$.

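### The primary comparison is a valid but unadjusted t-test; pre-specifying ANCOVA on the pre-treatment PSA growth rate is a cheap improvement whose gain depends on a correlation the documents do not give

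*Combined protocol and SAP*

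**What the plan says.** Section 8.1.1 powers the primary comparison "with a two-tailed 0.05 significance level two-group t-test". With 17 patients per arm, "there would be 80% power to detect a difference between the arms" of a size "equal to 1 SD of the difference from baseline to 7 months", on the condition "if the growth rate changes in the two arms had the same standard deviation". Section 8.1.4 again names Student's t-test for sample comparisons. Neither section, nor any other, names a covariate, a stratified test or a model for the primary comparison.

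Section 2.4 randomises 1:1, "stratifying for PSA doubling time using a computerized randomization process", with the cut at 6 months. Section 8.1.1 mentions this factor once, as a feature of the design.

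Each patient brings a pre-treatment value. Section 2.1.1 states: "Patients must have a PSA doubling time of 12 months or less", and it also requires a rising PSA confirmed by three values. Section 8.1.3 links doubling time to growth rate: g "equals \ln_2 divided by the time for the growing component to double".

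The analysed variable is described in three ways. Section 8.1.1 gives a change in growth rate from month 3 to month 7, and also a difference from baseline to month 7. Section 3.1 gives the re-growth rate at 7 months. Baseline is not defined for the growth rate.

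**The concern.** The stratification factor is a two-level cut of a pre-treatment growth measure, and the outcome is a growth measure in the same patients. If the two are correlated, stratified allocation balances part of the outcome's variance between the arms, but a plain t-test still counts that variance in its error term. The standard error is then too large for the design and the real type I error falls below 5%. Any chance imbalance in the continuous doubling time within strata also stays uncorrected. In a trial of 34 evaluable patients with one powered comparison, this could cost useful precision.

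Leaving the matter open also invites a choice between adjusted and unadjusted results after the data are seen.

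**Working it through.** **Inputs from section 8.1.1.** n = 17 per arm, standardised difference 1.0, equal SDs, two-sided alpha 0.05.

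**Assumed.** The correlation rho between the pre-treatment growth rate and the analysed variable. The documents give none, so it is varied from 0 to 0.7. The 1 SD is taken as the unadjusted within-arm SD of the analysed variable.

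**1. The plan's figure.** Two-sample t-test: df = 32, noncentrality = 1 × √(17/2) = 2.915, critical value 2.037. Power is 80.7%. With 16 per arm it is 78.1%. The stated 80% therefore reproduces, and 17 is the smallest sufficient number.

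**2. ANCOVA power.** With k covariates the residual variance is multiplied by (1 − rho²). Estimating the covariates in N = 34 patients inflates the variance of the arm difference on average by 1 + k/(N − k − 3), which is 1.033 for k = 1 and 1.069 for k = 2. Degrees of freedom are 32 − k. The effective standardised difference is 1/√[(1 − rho²) × inflation].

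Example, rho = 0.5 and k = 1: 1/√(0.75 × 1.033) = 1.136, noncentrality 1.136 × 2.915 = 3.31 on 31 df, power 89.4%.

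| rho | t-test | growth rate only (k = 1) | growth rate + stratum (k = 2) |
|---|---|---|---|
| 0 | 80.7% | 79.3% | 77.9% |
| 0.3 | 80.7% | 83.0% | 81.6% |
| 0.5 | 80.7% | 89.4% | 88.3% |
| 0.7 | 80.7% | 97.3% | 96.9% |

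The formula depends on rho², so the sign does not matter. ANCOVA breaks even at rho² = 0.034 with one term (rho about 0.19) and 0.068 with two (rho about 0.26).

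The difference detectable with 80% power is 0.99 SD for the t-test. At rho = 0.5 it is 0.87 SD with one term and 0.89 SD with two. If the covariate is useless it rises to 1.01 SD and 1.03 SD.

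**3. Simulation with stratified allocation.** The formula ignores the balance that stratification provides, so it was checked by simulating normal data with the stratum cut at the median. With permuted blocks of 4 (8,000 runs per setting), power at rho = 0, 0.3, 0.5 and 0.7 was:
- t-test: 80.9%, 81.4%, 82.4%, 83.4%
- growth rate only: 80.2%, 83.3%, 89.8%, 97.4%
- growth rate plus stratum: 79.3%, 82.5%, 89.1%, 97.0%

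The one-term gain is thus about 7 points at 0.5 (89.8 − 82.4) and 14 at 0.7 (97.4 − 83.4), slightly less than the formula's 9 and 17.

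**4. Type I error.** In the same simulation the t-test rejected in 5.0%, 4.3%, 3.7% and 1.8% of null trials. A second simulation with balanced pairs within strata (6,000 runs) gave 5.0%, 4.3%, 3.2% and 2.3%. ANCOVA stayed between 4.9% and 5.5% in both. A rough calculation agrees. With a median cut the between-stratum share of variance is rho² × 2/π, which is 0.159 at rho = 0.5. The critical value then acts like 2.037/√(1 − 0.159) = 2.22, a two-sided error of about 3.4%.

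**5. If the variable is already a change from the pre-treatment rate.** With equal variances, the change score has variance 2σ²(1 − rho) and ANCOVA has σ²(1 − rho²), a ratio of (1 + rho)/2. Taking the 1 SD as that of the change score, ANCOVA with the growth rate alone has 93.1%, 89.4%, 85.4% and 81.3% power at rho = 0.3, 0.5, 0.7 and 0.9, against 80.7%. Here the gain shrinks as rho rises.

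**The case against.** The strongest reply is that nothing in the plan is wrong. Under randomisation the unadjusted t-test gives an unbiased comparison, its type I error does not exceed the nominal level, and the sample size fits the stated test. In a pilot study, adjustment is optional. All of this stands.

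A reader might go further and infer three things that the documents do not support.

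- **That adjustment costs nothing.** Subtracting two degrees of freedom alone would suggest almost no loss at zero correlation. Estimating two covariates in 34 patients also inflates the variance, and power falls to 77.9% by formula or about 79% with stratified balance. At correlations up to about 0.2 the two-term model does no better than the t-test.
- **That a strong predictor is being discarded.** No section reports how pre-treatment growth relates to re-growth after enzalutamide. The 12-month ceiling on doubling time narrows its range. The three confirming PSA values may span as little as one month, so the entry slope may be noisy. Both could weaken the correlation.
- **That the stratification factor is the baseline value of the outcome itself.** Section 8.1.3 defines g as growth during treatment, from a curve normalised to day 0. Doubling time at entry is a quantity of the same kind, but the identity is not established. If the intended variable is a change from the pre-treatment rate, that rate is already used by subtraction.

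The last point limits the claim but does not remove it. For the month 3 to month 7 change, and for the rate at month 7, the pre-treatment rate is unused. For a change from the pre-treatment rate, subtraction is generally a less efficient use of it than regression (step 5). No reading brings the stratum into the analysis.

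**Conclusion.** The point holds as a cheap improvement, not as an error. The planned test is valid and correctly powered for what it is. If pre-treatment growth is correlated with the analysed variable, the test is conservative and inefficient: type I error is about 4.3% at a correlation of 0.3 and about 2% at 0.7.

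Adjusting for the continuous pre-treatment growth rate changes power by −1 to 0 points at a correlation of 0, +2 at 0.3, +7 to +9 at 0.5 and +14 to +17 at 0.7. Adding the stratum gains nothing further in these calculations, because it is a cut of the same doubling time.

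These figures rest on an assumed correlation, roughly normal data, a stratum cut at the median, and the plan's 1 SD being the SD of whichever variable is finally chosen. They apply to the trial only once that variable is named.

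**What to change.** In section 8.1.1:

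1. State one primary growth-rate variable and define its baseline, reconciling the month 3 to month 7 change, the difference from baseline to month 7, and the section 3.1 rate at 7 months.
2. Make the primary analysis an ANCOVA of that variable on arm, with the continuous pre-treatment growth rate (ln 2 divided by PSA doubling time at entry) as covariate. The randomisation stratum may be added to reflect the design, but it is largely redundant with the continuous rate and raises the break-even correlation from about 0.19 to about 0.26.
3. Report the adjusted difference with its 95% CI, and give the unadjusted t-test as a sensitivity analysis. Align section 8.1.4 with this.
4. Fix this before the arms are compared. The power statement can stay as written for the unadjusted test, with the range above as supporting information.

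The cost is a few sentences, one degree of freedom (two with the stratum), and about 1 to 3 points of power if the covariates prove uninformative. No patients, visits or assays are added.

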8.1.2 Halting Rules

The study will be halted for review of changes to the protocol and consent if either of the following is met:

- One occurrence of grade 5 toxicity attributed to the treatment regimen.
- Two occurrences of grade 4 toxicity attributed to the treatment regimen.

8.1.3 The regression-growth equation

The equation is $f(t) = \exp(-d * t) + \exp(g * t) - 1$ (A) where \exp is the base of the natural logarithm, $e = 2.7182$, and $f(t)$ is the tumor (or in MTC calcitonin) measurement at time t in days, normalized to (divided by) the tumor measurement at day 0, the time at which treatment is commenced. Rate constant d (decay, in days^{-1}) represents the exponential decrease/regression of the a serum tumor marker (i.e. PSA) signal during therapy. Rate constant g (growth, also in days^{-1}) represents the exponential growth/regrowth of the tumor during treatment. These rate constants may be expressed in terms of half-lives and doubling times. Thus, d equals $\ln_2(0.693)$ divided by the time it takes for the regressing part to shrink by half, whereas g equals \ln_2 divided by the time for the growing component to double. (44)

Two earlier papers depict theoretical curves depicting the separate components of Equation (A) and how these combine together to give the time dependence of the tumor size, f . (44) When the data showed a continuous decrease from the time of treatment start, so that only the regression parameter d was found to differ significantly from zero with $P < 0.05$, Equation (A) was replaced by the following reduced form, with the growth rate constant eliminated: $f(t) = \exp(-d * t)$ (B) When tumor measurements showed a continuous increase, so that only the growth parameter g was found to differ significantly from zero with $P < 0.05$, Equation (A) was replaced by the following reduced form, with the decay constant eliminated: $f(t) = \exp(g * t)$.

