3 STUDY IMPLEMENTATION

3.1 STUDY DESIGN

- This is a randomized Pilot trial of enzalutamide vs. enzalutamide and PSA-TRICOM in patients with nmCSPC prostate cancer. Thirty-four patients will be enrolled.
- Enzalutamide will be given at the standard dose of 160 mg daily for 3 months (7). PSA-TRICOM will be administered identical to the Phase III dosing with vaccine given week 1 (vaccinia-PSA-TRICOM, 2x10⁸ infectious units subcutaneously) and then fowlpox-vaccine (1x10⁹ infectious units subcutaneously) on weeks 3 and 5

followed by monthly fowlpox-vaccine (1×10^9 infectious units subcutaneously) for a total of 5 months (including vaccinia, vaccine is administered over 6 months).

- Patients will be followed for PSA recovery after enzalutamide has been discontinued. Patients who do not develop a 25% decline in PSA after 3 months will not be evaluated for tumor re-growth and additional patients will be enrolled to evaluate for that endpoint.
- Patients who have been on study for at least 7 months without PSA equaling or exceeding the value at study entry, and whose PSA subsequently (beyond 7 months) returns to or exceeds the value at study entry, may be retreated with a 3-month course of Enzalutamide.
- Patients who continue to be followed for rising PSA after completing either one or 2 courses of enzalutamide but have not required ADT may be followed after treatment. Such visits may occur at 4 week intervals based on logistics and clinical parameters (i.e. PSA velocity) once patients have exceeded their baseline PSA value. This approach is consistent with the clinical management of such non-metastatic patients (rising PSA and not on ADT.)
- The primary endpoint of this trial will be a comparison of the tumor re-growth rates at 7 months. This time frame should be sufficient to evaluate immune effect on the re-growth rate given that the ECOG 9802 analysis demonstrated a significant change in tumor growth rate after starting PSA-TRICOM.
Secondary endpoints include growth rate at points other than 7 months, toxicity, immunologic responses to vaccine with enzalutamide and to enzalutamide alone in men with normal testosterone, and response to second course of enzalutamide. When possible, patients will be followed for TTP. End of study period will be 12 months in each arm (24 months if patients are eligible and elect to receive a 2nd course of enzalutamide).

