8.1.4 Data Analysis

For each patient an attempt to fit Equation (A) to each data set for which more than one data point is available. Curve fitting will be performed using Sigmaplot (Systat Software), or by

Version Date: 12/5/17

Abbreviated Title: Enzalutamide in non-met CSPC

using the Solver routine in an Excel spreadsheet. We will extract parameters g and d with their associated Student's t and P values. (44) Data will be analyzed in Excel (Microsoft) and in Sigmaplot 9.0. Linear regressions to evaluate the relationship between the growth rate constant, g , or other parameters will be implemented using the polynomial linear routine of Sigmaplot 9.0. Sample comparisons were performed by Student's t -test, using SigmaStat 3.5 (Systat Software), with P set at 0.05 for significance. (44)

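### The growth equation is anchored at the start of enzalutamide, so its g mixes nadir depth with the off-drug PSA re-growth that the trial sets out to compare

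*Combined protocol and SAP*

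**What the plan says.** Section 1.1.1 asks about PSA growth kinetics after enzalutamide is stopped. Section 3.1 says: "The primary endpoint of this trial will be a comparison of the tumor re-growth rates at 7 months". Section 8.1.1 places the comparison between discontinuation (month 3) and month 7. In its power statement, however, "there would be 80% power to detect a difference between the arms" refers to a difference "equal to 1 SD of the difference from baseline to 7 months", tested "with a two-tailed 0.05 significance level two-group t-test". That introduces a second starting point.

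The estimator is in 8.1.3, repeated in 1.2.10: f(t) = exp(-d·t) + exp(g·t) - 1, with PSA "normalized to (divided by) the tumor measurement at day 0, the time at which treatment is commenced". The constant g "represents the exponential growth/regrowth of the tumor during treatment". Two reduced forms follow. If the data fall continuously from treatment start and only d is significant, "Equation (A) was replaced by the following reduced form, with the growth rate constant eliminated". If they rise continuously and only g is significant, the form is exp(g·t).

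Section 8.1.4 applies the equation "to each data set for which more than one data point is available". It does not say which PSA values make up a data set. Appendix C stops enzalutamide at week 13 and schedules PSA then and at weeks 15, 17, 21, 25 and 29.

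**The concern.** Equation (A) describes one decay and one growth process, both running from day 0 under continuing treatment. Here the drug is withdrawn on day 84 and the question is the slope after that.

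By the later visits exp(-d·t) is close to zero, so f(t) is about exp(g·t) - 1, which for small g·t is about g·t. The fitted g is then roughly the PSA level, as a fraction of baseline, divided by days since day 0. That is a level and not a log slope. It rises with re-growth, but also with a shallower nadir.

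The effect that 1.2.9 wants to show is a one-SD difference in re-growth rate. If nadir variation widens the spread of g, that effect is less than one SD on the scale actually tested.

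**Working it through.** **1. The plan's own figure.** Two-sided 0.05 t-test, 17 per arm, difference of 1 SD. Noncentrality = 1 × √(17/2) = 2.92 on 32 df. Exact power is 0.807 and the required n is 16.7, so 17 per arm. The stated 80% reproduces.

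**2. What g measures if the fit starts at day 0.** Inputs from the documents:
- Visit days 0, 14, 28, 56, 84, 98, 112, 140, 168 and 196 (Appendix C).
- Nadir within 4 weeks (1.2.7).
- Enzalutamide stopped at day 84.

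Assumed course: PSA falls exponentially to nadir N (fraction of baseline) by day 28, stays at N to day 84, then follows N·exp(k·(t - 84)). Equation (A) is fitted by least squares without noise.

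With k = 0.02/day for everyone, PSA at day 196 is N × exp(0.02 × 112) = 9.39 N:

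| Nadir N | PSA at day 196 | Fitted g per day |
|---|---|---|
| 0.02 | 0.19 | 0.00059 |
| 0.05 | 0.47 | 0.0014 |
| 0.10 | 0.94 | 0.0026 |
| 0.20 | 1.88 | 0.0045 |

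Ratio: 0.0045 / 0.00059 = 7.6, with identical re-growth.

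The ranking can also reverse. A flat PSA at N = 0.10 (k = 0) gives g = 0.00067. Growth of 0.02/day from N = 0.02 gives 0.00059. The flat series needs a positive g because the model can hold a non-zero plateau only by ramping through it: exp(0.00067 × 84) - 1 = 0.06 and exp(0.00067 × 196) - 1 = 0.14, either side of 0.10.

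The only nadir figures in the documents come from bicalutamide: declines of 95.5% (1.2.1) and 96.5% (1.2.7). At N = 0.045 and a 60-day off-drug doubling time (k = 0.01155), g = 0.00066, about 6% of k. With that doubling time, moving N from 0.01 to 0.3 moves g from 0.00015 to 0.00351 (23-fold). With N fixed at 0.045, a 6-fold change in k (doubling time 180 to 30 days) moves g from 0.00039 to 0.00164 (about 4-fold).

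**3. Power for a 1-SD difference in off-drug re-growth.** None of these inputs is in the documents: median nadir 4% to 4.5%, k with mean 0.02 and SD 0.006 per day, about 10% PSA noise, 17 per arm. Ranges are over repeated simulations of 150 to 200 trials (Monte Carlo error 0.03 to 0.04):

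| SD of ln(nadir) | Power using g from day 0 |
|---|---|
| 0 | 0.72 |
| 0.25 | 0.67–0.68 |
| 0.5 | 0.41–0.50 |
| 0.8 | 0.25–0.31 |
| 1.0 | 0.17–0.23 |

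The ln(PSA) slope from day 84 gave 0.75 to 0.84 in the same settings.

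A wider noise-free grid (4,000 replicates; median nadir 0.045, 0.1 or 0.3; k mean (SD) 0.0116 (0.004) or 0.0231 (0.008); nadir reached at day 28 or 84) gave these powers on g:
- 0.74–0.81 with identical nadirs
- 0.54–0.76 at log-SD 0.25
- 0.27–0.65 at 0.5
- 0.10–0.49 at 1.0
- 0.07–0.38 at 1.5

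Testing k itself gave 0.80–0.83 throughout.

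**4. Type I error.** With no arm difference and nadir log-SD 0.8, the t-test on g rejected in 0.046 of trials.

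**The case against.** The strongest reply is that 8.1.4 leaves the data set open. A fit to off-drug PSA with time zero at week 13 is not excluded, and 8.1.3 already has a form for a rising series, exp(g·t). Re-anchored at week 13, that form had power 0.80 and 0.77, against 0.80 and 0.78 for the log slope (mean re-growth 0.02 and 0.012/day, SD 0.006). This stands as a remedy: no new model is needed. It does not rescue the text, because the only time origin stated is the start of treatment, and an analyst who follows it estimates something other than the stated endpoint.

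Four stronger readings are tempting, and the documents do not support them.

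- *The 80% is wrong.* It is defined as 1 SD of the analysed quantity and is correct for that.
- *g measures the nadir and not re-growth.* It measures both. With faster re-growth and nadir log-SD 0.5, the rank correlation of g was 0.81 with the true rate and 0.55 with the nadir.
- *Chance nadir differences would be read as a vaccine effect.* Arms are randomized, and chance nadir variation enters the within-arm SD. The exception is a vaccine effect on the nadir itself. That is possible because vaccination starts in week 1, and a difference in g could then be misread as slower re-growth.
- *The elimination rule would remove g for about 30% of Arm B.* That figure comes from dropping g whenever P ≥ 0.05. Section 8.1.3 also requires a continuous decrease from treatment start. In the same simulation, a significant decrease, the nearest analogue, occurred in 0.9% of Arm A and 7.8% of Arm B. What remains is that no value is defined for a patient without g, while the power statement assumes a growth rate change for every patient.

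The minimum of more than one data point matters little in practice, since PSA is scheduled at baseline and nine visits to week 29.

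**Conclusion.** The concern holds as a mismatch between estimator and endpoint. Sections 1.1.1, 3.1 and 8.1.1 ask about re-growth after enzalutamide; 8.1.3 and 1.2.10 anchor the only growth rate at its start; and 8.1.1 ties the 1 SD to a difference measured from baseline. Followed literally, the primary analysis can rank a patient with flat PSA above one with true growth.

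The misranking depends only on the assumed shape of the PSA course. The power loss depends on the spread of nadirs and of re-growth rates, which the documents do not give. It is small if nadirs are nearly identical and large if they vary widely. The only limit in the plan is the 25% decline needed for evaluability, which admits nadirs of up to 75% of baseline. The consequence is lost sensitivity to the intended effect, with false-positive control intact.

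**What to change.** In 8.1.3, 8.1.4 and 1.2.10:

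- Set time zero for the primary growth rate at enzalutamide discontinuation.
- Estimate it for each patient as the slope of ln(PSA) on days since then, from the values at weeks 13, 15, 17, 21, 25 and 29. The form exp(g·t) re-anchored at week 13 is a close equivalent; name one of the two as primary.
- Keep every evaluable patient's estimate, including zero and negative slopes, and do not drop g on a significance test.
- Keep Equation (A) from day 0 as a descriptive analysis.

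In 8.1.1, define the growth rate change as this slope and tie the 1 SD to it in place of the baseline-to-7-months difference. The sample size calculation then stands unchanged.

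The cost is SAP wording. All these PSA values are already scheduled, and no visits or patients are added. The change should be recorded before PSA is compared between the arms.
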